4.3 Subject Exclusion Criteria

A participant will be ineligible to participate on this study if any of the following criteria are met:

1. Age < 18
2. Unable to comply with study visits, research study visits, or is planning to relocate during the study.
3. Have any condition that the investigator considers a contraindication to study participation
4. Pregnancy or breast feeding
5. Decompensated liver disease (Child-Pugh C)
6. Imminent treatment for HCV
7. Aspartate aminotransferase (AST) or alanine aminotransferase (ALT) >2.5 times the upper limits of normal
8. Concomitant use of drugs known to impact or be impacted in terms of pharmacokinetics or drug-drug interactions with either raltegravir, dolutegravir, or maraviroc. This includes:
 - Inducers of UGT1A1 (such as rifampin, phenytoin, phenobarbital, rifabutin, St. John's wort)
 - CYP3A inhibitors (such as ketoconazole, itraconazole, clarithromycin, nefazodone, and telithromycin)
 - CYP3A inducers (such as rifampin, carbamazepine, phenobarbital and phenytoin)

4.4 Justification for Exclusion: Children and Pregnant Women

The study will be limited to adults \geq 18 years of age as HCV is predominately a disease in adults. Children and pregnant or breast-feeding women will not be enrolled because of the lack of immediate benefit for the patient with the added risk of blood draws associated with the study.

5 Study Schedule

5.1 Screening /Enrollment

Screening will occur at the IHV. Subjects who consent to the study will be enrolled. A health history will be reviewed and a physical exam will occur prior to the baseline research lab draw. Outside labs performed within the last six months may be used to determine eligibility.

5.1.1 Procedures to be performed at Screening/Enrollment

- Complete Medical History
- Complete Physical Examination - including body weight, height, and vital signs (temperature, pulse, respiratory rate, and blood pressure) must be obtained.
- Complete Medication History – A complete review of all medications and supplements the patient is currently taking.
- Urine Pregnancy test for women of child bearing potential
 - Female subjects of childbearing potential will have a urine pregnancy test (HCG) performed prior to the study start date. Women who are found to be pregnant will be excluded from the study.
- Blood for Screening Labs obtained within 6 months of study entry –
 - CBC with differential
 - Serum Chemistry
 - LFT's (including AST, ALT, Total bilirubin)
 - Hepatitis C Quantitative RNA
 - HIV-1 RNA PCR
 - CD4 Cell Count

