4.1 Rationale for Subject Selection

Subjects of both genders will be considered for inclusion in this study. There will be no racial, ethnic, or gender discrimination. Persons in jail or prison are not eligible for this study. Women will not have research procedures while pregnant.

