5.4 Study visit, immediate start group only: Day 14 (Week 2 visit)

HCV VL will be obtained. Safety assessment will be performed (CBC with differential and CD4 and HIV viral loads. Patient reports of adverse effects). Labs can be completed up to 2 days later.

5.5 Study visits, immediate start group only: Day 21/week 3

HCV VL will be obtained. Labs can be completed 2 days later.

5.6 Study visit, both groups: Day 28/week 4

HCV VL and PBMC, plasma, serum and Paxgene RNA for storage will be obtained. Labs can be completed 2 days later.

Immediate start group: Maraviroc will be discontinued at day 28/week 4.

5.7 Washout period, week 4 through to week 8

5.8 Study visit, both groups: Day 56/week 8

HCV VL and PBMC, plasma, serum and Paxgene RNA for storage will be obtained.

Delayed start group: A review of medical history and medication history will be performed to evaluate for any interim changes from screening visit. Physical exam will be performed. HCV VL and PBMC, plasma, serum, and Paxgene RNA for storage will be obtained. Maraviroc will be started.

5.9 Study visits, delayed start group only: Day 57, 58, 60, 63, 70 (week 10), 77 (week 11)

HCV VL will be obtained

Safety assessment at day 70/week 10 (on week 2 after initiating maraviroc).

Weeks 10 and 11 labs can be completed up to 2 days later.

5.10 Study visit, both groups: Day 84/Week 12

HCV VL and PBMC, plasma, serum. and Paxgene RNA for storage will be obtained. Visits can be completed up to 2 days later.

Delayed start group: Maraviroc will be discontinued. Safety assessment.

Immediate start group: **End of study participation.** Safety assessment.

5.11 Study Visit, delayed start group only: Day 112/week 16

HCV VL and PBMC, plasma, serum, and Paxgene RNA for storage will be obtained. Safety assessment. **End of study participation.** Visit can be completed up to 2 days later.

6 Study Procedures/Evaluations

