6.1 Clinical Evaluations

Participants will be seen by a study team member at screening, and maraviroc start dates (day 0 for immediate start group, and day 56/week 8 for the delayed start group) for a review of health history.

Participants will also be seen by a study team member every weeks while taking maraviroc (day 0, week 1, week 2, week 3 week 4 for the immediate start group, and Day 56/week8, week 9, week 10, week 11, week 12 for the delayed start group) and every 4 weeks prior to starting, and after completing maraviroc (week 8 and week 12 for the immediate start group, and day 0, week 4, and week 16 for the delayed start group) for adverse event monitoring.

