6.2 Laboratory Evaluations

Blood will be collected by standard blood drawing techniques. All laboratory assays will be done at University of Maryland Medical Center or at the IHV research lab facilities depending upon the assay. Stored samples will be processed and stored at the IHV research laboratories.

Screening: CBC with differential; creatinine and hepatic function tests including; albumin, alkaline phosphatase, aspartate aminotransferase (AST), alanine aminotransferase (ALT) will be collected or outside records showing eligibility will be used. Hepatitis serologies and viral loads will be completed if medically indicated.

Research Visits:

At the first study visit the following tests will be done:

- Baseline HCV VL
- Serum storage (10 ml)
- Plasma storage (6ml)
- DNA paxgene will be collected (8.5ml)
- RNA paxgene will be collected (2.5ml)
- Peripheral blood mononuclear cell (50 ml)

At all study visit including the first study visit the following **clinical laboratory** tests will be done:

- Hepatitis C viral load

After the first 2 weeks while on maraviroc (day 14/week 2 for the immediate start group; and day 70/week 10 for the delayed start group) the following **safety assessment** will be done:

- HIV VL, CBC with differential, and CD4 count (24.5 ml)
- Patient reports of adverse effects

Every week while taking maraviroc, and once every 4 weeks prior to starting, and after completing maraviroc, the following **clinical assessments** will be done:

- Adverse event monitoring (patient reports of adverse effects)
- Medication review

At study visits every 4 weeks including the first study visit the following blood specimens may be collected for **research laboratory** storage and tests (total 68.5 ml research, or about 4.6 tablespoons):

- RNA paxgene (2.5ml)
- Peripheral blood mononuclear cell (50 ml)
- Serum storage (10 ml)
- Plasma storage (6ml)

Outside Tests: Tissue may be requested from liver biopsies done for clinical purposes; imaging, FibroScan or other liver evaluation results may also be requested from outside providers with subject consent.

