9.4 Withdrawal of a Subject

A participant may withdraw from the study at any time. As part of their duties to ensure that research participants are protected, the IRB, IHV, or other government agencies may discontinue the study at any time. Voluntary withdrawal from the protocol may occur at any time at the request of either the participant or the PI. If a request is made to withdraw from the protocol, all further planned study procedures will be immediately cancelled and further follow-up will be terminated. Samples and data collected prior to this request will be stored and used as outlined in the protocol unless a specific request is made by the participant to remove all of their samples from the study. Data already obtained from the participant's samples will not be discarded. In addition, participants with poor compliance and/or failure to present for follow-up visits may be withdrawn from the study at the discretion of the PI.

If a patient becomes pregnant during the course of the study, the investigator, in consultation with the patient, should consider whether the potential benefit justifies the potential risk to the fetus of continuing the study therapy. If it is determined that the potential benefit does not outweigh the potential risk to the fetus, the patient should be discontinued from the study.

Should a subject develop evidence of HIV virologic breakthrough, or decline in CD4 to less than 200 (if above 200 at baseline) during the study they will be evaluated by their primary HIV provider and may be withdrawn from the study at the discretion of the PI.

Discontinuation of maraviroc will be considered in any patient with signs or symptoms of acute hepatitis, in particular if drug-related hypersensitivity is suspected or with increased liver transaminases combined with rash or other systemic symptoms of potential hypersensitivity (e.g. pruritic rash, eosinophilia or elevated IgE).

Should a subject be started on anti-HCV therapy while in the study, maraviroc will be discontinued and the subject will be withdrawn from the study.

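### The body text lists no pregnancy test before the delayed group's first maraviroc dose at day 56, when the screening test is at least 56 days old; the unseen delayed-start schedule should be checked first

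*Combined protocol and SAP*

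**What the plan says.** Section 5.1.1, under screening and enrolment, states: "Female subjects of childbearing potential will have a urine pregnancy test (HCG) performed prior to the study start date". Women found pregnant at that point are excluded. Section 4.3 lists "Pregnancy or breast feeding" as an exclusion, and section 4.1 adds a general rule: "Women will not have research procedures while pregnant". Section 4.4 explains that pregnant women are not enrolled "because of the lack of immediate benefit for the patient with the added risk of blood draws associated with the study".

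The delayed group takes no maraviroc until day 56. Before then, section 6.1 schedules contacts at "and day 0, week 4, and week 16 for the delayed start group) for adverse event monitoring"; of these, day 0 and week 4 precede the first dose. Section 6.2 defines the content of such contacts as patient-reported adverse effects and a medication review. For day 56, section 5.8 says: "Delayed start group: A review of medical history and medication history will be performed to evaluate for any interim changes from screening visit". It then lists a physical exam, an HCV viral load and storage samples, after which the drug is started.

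For pregnancy on study, section 9.4 asks the investigator, with the patient, to "consider whether the potential benefit justifies the potential risk to the fetus of continuing the study therapy".

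**The concern.** The protocol checks for pregnancy once, at entry. For the immediate group that can fall close to the first dose. For the delayed group the same check comes eight weeks or more before the first dose, and the text lists nothing to refresh it. Section 5.8 does re-examine these participants before dosing, specifically for changes since screening, but it leaves out the one test that would confirm that an entry exclusion still does not apply.

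If 5.8 is followed as written, a woman who conceives after screening could start maraviroc and continue with blood draws while the pregnancy is unrecognised. Section 7.2 states that participants gain no direct clinical benefit, so nothing on her side offsets an exposure that the protocol means to avoid.

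**Working it through.** The plan states no figure on this point. The check is a reading of the schedule plus one subtraction.

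**Inputs**
- Latest day for the listed HCG: day 0 (5.1.1, before study start).
- First maraviroc dose, delayed group: day 56 (5.8, 6.1). Section 5.8 gives no early window for this visit.
- First maraviroc dose, immediate group: day 0 (5.3.1).

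**Delayed-group contacts up to the first dose, body text only**

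| Contact | Listed content | HCG listed |
|---|---|---|
| Screening (5.1.1) | History, exam, medication history, screening labs, urine HCG | Yes |
| Day 0 (5.3.1, 6.1, 6.2) | HCV viral load, storage samples, adverse events, medication review | No |
| Day 28 (5.6, 6.1, 6.2) | HCV viral load, storage samples, adverse events, medication review | No |
| Day 56 (5.8) | Interim history, medication history, physical exam, HCV viral load, storage samples, first dose | No |

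**Gap from test to first dose**
- Delayed group, minimum: 56 − 0 = 56 days.
- Immediate group, minimum: 0 − 0 = about 0 days.
- Delayed group with an HCG added at day 56 before dosing: 56 − 56 = 0 days.

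**Meaning of study start.** The phrase in 5.1.1 could be taken to mean the start of the drug, which for the delayed group would be day 56. But it stands under screening procedures, and 6.1 uses a separate term for the dates on which maraviroc begins. The screening reading is the natural one.

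**Number affected.** With 1:1 allocation (5.2), the delayed group is about 10 / 2 = 5 participants, or 7 or 8 at the accrual ceiling of 15. The documents do not say how many would be women of childbearing potential. It could be none.

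**The case against.** The strongest reply is that the page that would settle the matter is missing. The supplied Appendix B breaks off at the hepatic panel row of the immediate-start table, and no delayed-start table is visible. The rows that can be seen do not show even the screening HCG that 5.1.1 requires, so any pregnancy-test row would lie in the lost part. Silence in the visit sections is also weak evidence here: Appendix B gives a targeted physical exam, height, vitals and weight at day 0, none of which appears in 5.3.1. This stands. A day 56 HCG in Appendix B cannot be ruled out, so the point is conditional.

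Second, pregnancy is partly covered elsewhere. The 4.1 rule is not limited to enrolment, the day 56 history and exam may bring a pregnancy to light, and 9.4 applies to pregnancies arising at any time during the study. These reduce the gap, but none of them schedules a test. Section 9.4 operates once a pregnancy is known and is framed around continuing therapy rather than starting it.

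Third, a reader might infer a larger harm than the documents support:
- **Fetal toxicity.** Section 9.4 mentions risk to the fetus only in general terms, and 7.1 lists none for maraviroc.
- **A probability of pregnancy by day 56.** This needs a conception rate and a count of eligible women, and neither is given.
- **A worst case** of 9 draw visits (days 56, 57, 58, 60, 63, 70, 77, 84, 112) and 3 × 68.5 = 205.5 ml of storage blood. This requires the pregnancy to go unnoticed through the contacts at days 63, 70, 77, 84 and 112.
- **A gap of several months more than 56 days.** Section 5.1 accepts outside labs up to six months old, but the text does not say that this covers the urine HCG.

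**Conclusion.** The point holds in a limited, conditional form. In the body text (5.1.1, 5.3 to 5.11, 6.1, 6.2), the only scheduled HCG is at least 56 days old when a delayed-start woman takes her first dose. The pregnancy exclusion and the 4.1 rule then rely on history and exam alone at that moment. This rests on reading study start in 5.1.1 as the start of the study, and on the unseen delayed-start schedule not already listing the test.

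It is a minor safety correction. It concerns avoidable exposure and phlebotomy in a study without direct benefit, in a group of about 5 that may include no woman of childbearing potential. It would be wrong to conclude that the protocol as a whole omits the test, or that a measurable risk has been shown: the first cannot be verified from the supplied text, and the second has no inputs in it.

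**What to change.** First confirm what the delayed-start part of Appendix B lists at day 56. Then add to 5.8, and to Appendix B if it is not there: *Women of childbearing potential will have a urine HCG at day 56 before dosing; maraviroc is started only after a negative result, and a woman who tests positive is not started and has no further research procedures (4.1).* If Appendix B already has the test, 5.8 should still be brought into line with it.

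**Cost.** One urine test per eligible woman in the delayed group: 0 to about 5 tests at N = 10, or 0 to 8 at the ceiling of 15. The visit already includes a physical exam.

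**Downside.** A woman who tests positive is never dosed and so does not enter the section 11.2 analysis set, which requires at least one dose. One such case takes the set from 10 to 10 − 1 = 9 and the delayed group from about 5 to 4. The accrual ceiling leaves room for 15 − 10 = 5 more participants, but the text states no replacement rule.

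**What it leaves open.** The change does not address conception after dosing has begun. It also does not settle the tension between 9.4, which allows therapy to continue in pregnancy after a benefit-risk discussion, and 4.1, which bars research procedures.

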5.2 Randomization

Enrolled participants will be randomized to the immediate start or delayed start group in a 1:1 fashion at time of enrollment.

5.3 Day 0 to Day 7

5.3.1 Study visit, all subjects: Baseline Visit – Day 0

Once eligibility is known, *all subjects* will have baseline research sample collection of HCV VL, and PBMC, plasma, serum and Paxgene RNA and DNA for storage. Maraviroc will be initiated for participants randomized to the immediate start group.

5.3.2 Study Visits, immediate start group only: Days 1, 2, 4 and 7

HCV VL will be obtained at days 1, 2, 4 and 7. Day 7 labs can be completed up to 1 day later.

5.4 Study visit, immediate start group only: Day 14 (Week 2 visit)

HCV VL will be obtained. Safety assessment will be performed (CBC with differential and CD4 and HIV viral loads. Patient reports of adverse effects). Labs can be completed up to 2 days later.

5.5 Study visits, immediate start group only: Day 21/week 3

HCV VL will be obtained. Labs can be completed 2 days later.

5.6 Study visit, both groups: Day 28/week 4

HCV VL and PBMC, plasma, serum and Paxgene RNA for storage will be obtained. Labs can be completed 2 days later.

Immediate start group: Maraviroc will be discontinued at day 28/week 4.

5.7 Washout period, week 4 through to week 8

5.8 Study visit, both groups: Day 56/week 8

HCV VL and PBMC, plasma, serum and Paxgene RNA for storage will be obtained.

Delayed start group: A review of medical history and medication history will be performed to evaluate for any interim changes from screening visit. Physical exam will be performed. HCV VL and PBMC, plasma, serum, and Paxgene RNA for storage will be obtained. Maraviroc will be started.

5.9 Study visits, delayed start group only: Day 57, 58, 60, 63, 70 (week 10), 77 (week 11)

HCV VL will be obtained

Safety assessment at day 70/week 10 (on week 2 after initiating maraviroc).

Weeks 10 and 11 labs can be completed up to 2 days later.

5.10 Study visit, both groups: Day 84/Week 12

HCV VL and PBMC, plasma, serum. and Paxgene RNA for storage will be obtained. Visits can be completed up to 2 days later.

Delayed start group: Maraviroc will be discontinued. Safety assessment.

Immediate start group: **End of study participation.** Safety assessment.

5.11 Study Visit, delayed start group only: Day 112/week 16

HCV VL and PBMC, plasma, serum, and Paxgene RNA for storage will be obtained. Safety assessment. **End of study participation.** Visit can be completed up to 2 days later.

6 Study Procedures/Evaluations

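### The visit text lets delayed-start patients take their first maraviroc dose at day 56 on a screening AST/ALT that is 8 to about 34 weeks old; a pre-dose check would cost little

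*Combined protocol and SAP*

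**What the plan says.** **Entry limit.** Exclusion 7 in section 4.3 reads "Aspartate aminotransferase (AST) or alanine aminotransferase (ALT) >2.5 times the upper limits of normal".

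**Age of the deciding result.** Section 5.1.1 calls for "Blood for Screening Labs obtained within 6 months of study entry", and AST and ALT are among them. Section 5.1 adds "Outside labs performed within the last six months may be used to determine eligibility". Section 6.2 says of the screening tests, AST and ALT included, that they "will be collected or outside records showing eligibility will be used".

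**First dose.** On day 0, under 5.3.1, "Maraviroc will be initiated for participants randomized to the immediate start group". The delayed group starts at day 56. Section 6.1 has patients seen at screening and at both "maraviroc start dates (day 0 for immediate start group, and day 56/week 8 for the delayed start group) for a review of health history".

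**What precedes the day 56 dose.** For the delayed group section 5.8 says "A review of medical history and medication history will be performed to evaluate for any interim changes from screening visit", followed by "Physical exam will be performed. HCV VL and PBMC, plasma, serum, and Paxgene RNA for storage will be obtained. Maraviroc will be started".

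**Liver risk.** Section 7.1 counts raised liver tests among the possible serious side effects and allows that coinfected patients might be at higher risk. It also reports similar rates of liver-test abnormality on maraviroc and placebo.

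**The concern.** Section 5.8 looks for changes since screening before the delayed group is dosed, but by history, medication review and examination only. The one numerical liver criterion in the exclusion list is not among the things refreshed, although blood is drawn at that visit. A patient whose AST or ALT had risen above 2.5 times the limit since screening, without symptoms, could be dosed with nobody knowing.

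Two things are at stake. The first is patient safety in a group that all have HCV and may include cirrhotics (4.2). The second is interpretation: safety of adding maraviroc is a secondary objective (2.2), and without a current pre-dose value an abnormality found later cannot be separated from one that was already there. The HCV viral load endpoint is not affected.

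**Working it through.** The plan gives no figure for the age of the AST/ALT at first dose, so there is none to reproduce. The check has two parts.

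**1. Is AST/ALT listed anywhere between screening and the day 56 dose?**

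| Delayed-group visit | Section | Laboratory content listed |
|---|---|---|
| Day 0 | 5.3.1 | HCV viral load, stored samples |
| Week 4 | 5.6 | HCV viral load, stored samples |
| Day 56, before dosing | 5.8 | HCV viral load, stored samples |
| Day 70, first safety assessment | 5.9, 6.2 | HCV viral load, HIV viral load, CBC, CD4 |

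Section 6.2 has five post-screening lists: first visit, all visits, week 2 safety, clinical assessments and four-weekly storage. None names AST or ALT. The delayed group's first safety assessment comes at day 70, which is 70 − 56 = 14 days after the first dose, and it does not include liver enzymes either. Serum is stored at day 56, but no AST/ALT test on it is specified.

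**2. How old can the value on file be?**

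Age at first dose = (study entry − laboratory date) + (day 0 − study entry) + day of first dose.

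Inputs: a look-back of up to six months before study entry (5.1.1); first dose at day 0 or day 56 (5.3.1, 5.8). Day 0 is taken as study entry, which is an assumption.

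- Delayed group, minimum: 0 + 0 + 56 days = 56/7 = 8.0 weeks.
- Delayed group, maximum with six months as 26 weeks: 26 + 8 = 34.0 weeks.
- The same with six calendar months (181 to 184 days): (181 + 56)/7 = 33.9 to (184 + 56)/7 = 34.3 weeks.
- The same with 6 × 30 days: (180 + 56)/7 = 33.7 weeks.
- Immediate group: 0 to about 26 weeks (184/7 = 26.3 at most).

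Only the extra 8 weeks is specific to the delayed group. The documents set no limit on the gap between study entry and day 0. A gap of 14 days, for illustration, gives (182.6 + 14 + 56)/7 = 36.1 weeks, so 34 is if anything low as a maximum.

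**Patients concerned.** With 1:1 randomization (5.2), 10/2 = 5 delayed-start patients; at the ceiling, 15/2 = 7.5, so 7 or 8.

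The documents give no rate at which AST or ALT crosses the limit between entry and day 56, so the number of patients who would be affected cannot be calculated.

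**The case against.** **The schedule table is incomplete in the copy reviewed.** Appendix B stops inside the immediate group's hepatic-panel row, just after the screening mark, and the delayed group's schedule is absent. A panel at first dose cannot be ruled out in either arm. The section text is also not a closed list: Appendix B gives the immediate group a targeted examination and vital signs on day 0 that 5.3.1 does not mention, and 5.10 and 5.11 add safety assessments beyond the week 2 one in 6.2. This objection stands, and it limits the point to what the section text permits.

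**Newer results may exist.** Routine care may supply them, and 6.2 allows outside liver evaluations to be requested. True, but nothing requires a newer value before the day 56 dose.

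**Safeguards exist and the risk is small.** The day 56 history and examination, adverse event monitoring (6.1), the investigator's discretion under exclusion 3 and the stopping rule in 9.4 all help, and 7.1 reports similar liver-test abnormality rates on maraviroc and placebo. This keeps the point modest. These safeguards rest mainly on signs or symptoms, however, and would not show a symptom-free rise.

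**Exclusion 7 is an entry criterion, and a dosing hold is something the protocol never sets.** Also true. A reader might infer that dosing at day 56 on an old value breaks the six-month rule or contradicts the plan. It does neither, because the window is tied to study entry, not to first dose. The hold is a proposed addition.

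**Conclusion.** The point holds as a low-cost safety improvement. On the section text, delayed-start patients may take their first dose on an AST/ALT 8 to about 34 weeks old, which concerns 5 patients at N=10 and 7 to 8 at the ceiling of 15. The range describes what the text allows, not what every patient will have. It assumes that day 0 is study entry, that six months is about 26 weeks and that no newer result has been obtained.

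Two stronger readings are tempting and unsupported. One is that the protocol never measures liver enzymes after screening; the cut-off Appendix B leaves that open. The other is that delayed-start patients face a material, quantifiable hazard; the documents supply no crossing rate, and the comparison in 7.1 points to a small one. Nor is this purely a delayed-group matter, since the immediate group may be dosed on a value up to about 26 weeks old.

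The change is worth making because section 5.8 already sets out to refresh patient status before dosing, the blood is already being drawn, and the threshold is the protocol's own.

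**What to change.** - **Test.** In 5.8 and 6.2, add AST/ALT to the day 56 draw for delayed-start patients, or take it a few days earlier so that the result is in hand.
- **Hold.** Withhold the first dose if either value exceeds 2.5 times the upper limit of normal. State one retest, for example within 2 weeks, and release the patient once both are at or below the limit. If still above, do not dose, but keep the patient in follow-up and report held patients by arm.
- **Timing.** Count the day 57 to day 112 visits from the actual first dose, and take the pre-dose HCV viral load with that dose so that the kinetic baseline stays next to it.
- **Immediate group (optional).** Apply the same check at day 0 (5.3.1, 6.2), so that both arms follow one rule.
- **Leave alone.** The six-month window and the threshold in exclusion 7.
- **If Appendix B already schedules these panels,** align 5.8 and 6.2 with it and add only the hold rule.

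**Cost.** Wording changes, plus about 5 to 8 panels at day 56, or 10 to 15 in total (one per patient) if day 0 is included, before any retest. No new endpoint and no sample-size change; no new routine visit if the day 56 draw is used, though an earlier sample or a retest may need a separate one. There is a short wait for results and a possible shift in the schedule of a held patient. A patient held and never dosed would fall outside the analysis set in 11.2, which requires at least one dose; at N=10 each such patient is 1/10 = 10% of the sample. If the check is used in both arms, that can happen in either arm under the same rule.
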